4.4.1 Risk prediction

Risk prediction of ESKD in IgAN patients will be based on histology (MEST-C classification), eGFR, proteinuria, presence of hypertension at time of the kidney biopsy. We will use our IgAN CDSS tool (DialCheck).

By using a new designed tool, risk prediction will be done at different time of the clinical course of the disease: i) at the time of clinical and histological diagnosis; ii) after 4 and 8 months from the therapy in patients with active renal lesions; iv) after 10 months from the therapy in patients with chronic or moderate renal lesions. Then, every year during the follow-up.

4.5 Participant timeline

Total Study duration: approximately 6 years:

- Enrollment period: 3 years
- Treatment and Follow-up period: 3 years + 30 days.

Figure 2A and **2B** illustrate the time schedule of enrollment, interventions, assessments and visits for participants.

Figure 2A. SPIRIT 2013 STATEMENT OF THE ACiGAN STUDY: Time schedule of the enrolment, interventions, assessments and visits of the participants.

Time point	STUDY PERIOD																			
	Enrolment	Allocation	Post-allocation														End of Treatment	End of Study		
			t ₁	t ₂	t ₄	t ₆	t ₈	t ₁₂	t ₁₅	t ₁₈	t ₂₁	t ₂₄	t ₂₇	t ₃₀	t ₃₃	t ₃₆				
	- t ₁	t ₀															t ₃₆	30 days after last treatment		
Enrolment:																				
Eligibility screen	x																			
Informed consent	x																			
Kidney biopsy	x																			
Laboratory data	x																			
Allocation		x																		
Interventions:																				
(A) Cs+RASBs (4 months) → RASBs			●	—————														●		
(B) RASBs (4 months) →Cs+RASBs (4 months)→RASBs			●	—————														●		
Assessments:																				
Serum creatinine	x		x	x	x	x	x	x	x	x	x	x	x	x	x	x	x			
eGFR	x		x	x	x	x	x	x	x	x	x	x	x	x	x	x	x			
Daily proteinuria	x		x	x	x	x	x	x	x	x	x	x	x	x	x	x	x			
Adverse events	x		x	x	x	x	x	x	x	x	x	x	x	x	x	x	x		x	
Concomitant medications	x		x	x	x	x	x	x	x	x	x	x	x	x	x	x	x		x	
Outcome variables:																				
Proteinuria reduction (primary end point)						x	x	x	x	x	x	x	x	x	x	x	x	x		
eGFR slope reduction (secondary end point)			x	x	x	x	x	x	x	x	x	x	x	x	x	x	x	x		
Biological samples collection		x	x	x	x	x	x	x				x				x				

Figure 2B. SPIRIT 2013 STATEMENT OF THE CHRONIGAN STUDY: Time Schedule of the enrolment interventions, assessments and visits of the participants.

Time point	STUDY PERIOD															
	Enrolment	Allocation	Post-allocation												End of Treatment	End of Study
	- t ₁	t ₀	t ₁	t ₄	t ₈	t ₁₀	t ₁₂	t ₁₄	t ₁₈	t ₂₄	t ₂₇	t ₃₀	t ₃₃	t ₃₆	t ₃₆	30 days after last treatment
Enrolment:																
Eligibility screen	x															
Informed consent	x															
Kidney biopsy	x															
Laboratory data	x															
Allocation		x														
Interventions:																
(A) RASBs (4 months)→ Dapagliflozin +RASBs			●	—————											●	
(B) RASBs (4 months)→ Cs+RASBs(6 months)→RASBs			●	—————											●	
Assessments:																
Serum creatinine	x		x	x	x	x	x	x	x	x	x	x	x	x		
eGFR	x		x	x	x	x	x	x	x	x	x	x	x	x		
Daily proteinuria	x		x	x	x	x	x	x	x	x	x	x	x	x		
Adverse events	x		x	x	x	x	x	x	x	x	x	x	x	x		x
Concomitant medications	x		x	x	x	x	x	x	x	x	x	x	x	x		x
Outcome variables:																
Proteinuria reduction (primary end point)						x	x	x	x	x	x	x	x	x	x	
eGFR slope reduction (secondary end point)			x	x	x	x	x	x	x	x	x	x	x	x	x	
Biological samples collection		x	x	x	x	x		x		x				x		

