1.5. Overall risk and benefit statement

The major benefit for the IgAN patients enrolled in the present study will be a targeted therapy based on renal lesions described in the kidney biopsy report, given the existing equipoise for scientific studies that may assess the role of kidney biopsy in driving interventions, in light of significant empiric practice evidence and strong, consistent observational evidence supporting a potential causal link.

This may be an advantage for IgAN patients, in line with what is supported by the *MEST-C score* of the Oxford classification validated in the VALIGA study cohort (9).

To date, the current KDIGO guidelines do not consider the presence of active and chronic renal lesions at the time of the kidney biopsy for therapy decision, based on the lack of experimental trial data; this question seems highly relevant in view of pragmatic clinical practice knowledge and the results of cohort studies, their strength and consistency.

The potential risks and benefits of this trial are mainly related to study treatments and they are listed below; the actions/ways to mitigate the risks are specified, in brackets, in the section “Drug risks”.

Drug risks

Corticosteroids: hypertension (anti-hypertensive drugs), water retention (diuretics), hyperglycemia (antidiabetic drugs or insulin), muscle hypotrophy (daily exercise), hyperlipidemia (lipid-lowering agents), body weight increase (diet).

RASBs: allergy (anti-allergy drugs or low doses of corticosteroids), angioedema (corticosteroids), hypotension (dose reduction), hyperkalemia (diet or cation exchange resins), impairment of the renal function (dose reduction or temporary suspension), acute renal failure (drug suspension).

Dapagliflozin: allergy (anti-allergy drugs or low doses of corticosteroids), hyperlipidemia (lipid-lowering agents), hypoglycemia (drug suspension), impairment of the renal function (dose reduction or temporary suspension), acute renal failure (drug suspension).

Drug benefits

Proteinuria reduction, time-averaged proteinuria (TA-P) improvement, proteinuria slope reduction, eGFR slope reduction, delayed end-stage kidney disease.

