To our knowledge, this is the first study in which corticosteroids are administered immediately after the kidney biopsy in IgAN patients with active renal lesions. Based on the existing evidence from randomized clinical trials, the KDIGO guidelines suggest in those cases: RASBs for 3-6 months and then corticosteroids in presence of persistent proteinuria and $GFR >30$ ml/min/1.73 m². This therapeutic approach, although supported by evidence, may be a challenge based on empiric clinical knowledge supported also by findings of cohort studies. This demonstrates that after 3-6 months active renal lesions become chronic and consequently no association may be found between exposure to corticosteroids and clinical response for IgAN patients. In our randomized clinical study we compare the standard approach proposed by KDIGO guidelines (RASBs for 3-6 months followed by corticosteroids) vs a novel approach consisting of early corticosteroid therapy combined with RASBs from the beginning.

CHRONIgAN TRIAL

Patients with chronic (T1,2) or moderate renal lesions (M0,1; S0,1, E0, C0, T0) will be enrolled in a two-arm trial with 1:1 allocation ratio to compare Dapagliflozin combined with RASBs (experimental arm) versus corticosteroids combined with RASBs (control arm) after 4 run-in months of RASBs treatment. The enrolled patients will have proteinuria ≥ 0.5 g/day and GFR ≥ 30 ml/min/1.73 m².

Participants will receive study treatments by 4 weeks from the kidney biopsy.

Patients assigned to the experimental arm will receive RASBs therapy (4 run-in months) followed by Dapagliflozin (10 mg /day orally) combined with RASBs for a total of 32 consecutive months. Patients assigned to the control arm will receive RASBs therapy (4 run-in months) followed by oral corticosteroids therapy (prednisone) for six months (0.4 mg/kg body weight for 2 months and then gradual reduction of 5 mg/day for 4 months) and then RASBs alone for a total of 36 consecutive months.

This is a parallel group, two arm, superiority trial with 1:1 allocation ratio.

Rationale of the study design

We decided the combination Dapagliflozin and RASBs because recently, SGLT2is were administered in patients with type 2 diabetes and in other participants with CKD (some of them were affected by IgAN) (29-31). In these studies, the effect of SGLT2is was compared with a placebo.

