Patients will receive oral corticosteroids therapy for six months (prednisone 0.4 mg/kg body weight for 2 months and then gradual reduction of 5 mg/day for 4 months) combined with RASBs and, then, RASBs alone for a total of 36 consecutive months.

Rationale: To care the moderate and chronic renal lesions in non-responders to RASBs alone as suggested by the KDIGO guidelines (4,5).

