-Serum creatinine. Creatinine will be measured using enzymatic methods calibrated to the National Institute of Standards and Technology Liquid Chromatography Isotope Dilution Mass spectrometry method. Estimated (e) GFR creatinine will be estimated by the CKD-EPI formula (50). Moreover, we will calculate the slope of acute, chronic and total eGFR (51). Patients, categorized in CKD stage 1 to 3, will be included in the clinical study.

-Proteinuria. Patients will collect 24 hour urine for proteinuria and creatininuria. Values of >0.5 g/day will be considered abnormal. We will measure the time-average proteinuria (TA-P) (52) and the slope of proteinuria (53).

Serum creatinine, proteinuria, age and hypertension have a lower weight when histological lesions are not considered. This finding highlights the importance of the kidney biopsy, not only for diagnosis but for personalized treatment.

-Blood hypertension is defined when values are > 130/80 mmHg or in subjects treated with anti-hypertensive drugs. Treatment will also be conducted in hypertensive patients with blood pressure >130/80 and daily proteinuria more than 0.5 g. Sodium restriction is necessary.

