9.5 Collection of biological samples

In this project we will collect blood, kidney biopsy and urine samples from IgAN patients with acute renal lesions enrolled in the ACIgAN clinical study and from IgAN patients with chronic and moderate renal lesions enrolled in the CHRONIgAN trial. Blood and urine samples will be collected

in every patient on the same day before kidney biopsy will be performed and then during the clinical course of the disease. IgAN patients will be accurately stratified by the MEST-C classifications.

Blood and urine samples will be collected at different time (T) from patients during the follow-up of the CLlIgAN study:

- i) patients with active renal lesions: T0,T1,T2,T4,T6, T8,T12,T24, T36 months and
- ii) in patients with chronic and moderate renal lesions: T0,T1,T4,T8,T10,T14,T24,T36 months.

Blood samples. 10 ml of blood will be collected in PAXgene tubes for the isolation of peripheral blood leukocytes that will be used for transcriptomic studies.

Serum samples will be collected for the measurement of IgA, Gd-IgA1 and other biomarkers. Some of these biomarkers have been described as predictors of clinical outcome but none has been validated in prospective clinical studies. Therefore, we will measure some current biomarkers involved in the pathogenesis of the disease as Gd-IgA1 during the follow-up.

Urine samples. 30-50 ml of urine of the second morning urination will be collected for the isolation of urinary microvesicles.

Renal biopsy will be used for histological diagnosis and immunofluorescent technique. Then, transcriptomics will be performed in RNA eluted from 5 micron thickness sections for a total of 8 slides.

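### CHRONiGaN's visit table (Figure 2B) has no laboratory or adverse-event visit between study-drug start at month 4 and month 8, which conflicts with the three-monthly evaluation in Section 4.4

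*Protocol*

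**What the plan says.** Protocol Section 3 (CHRONiGaN) compares the two regimens "after 4 run-in months of RASBs treatment". The experimental arm's run-in is "followed by Dapagliflozin (10 mg /day orally) combined with RASBs for a total of 32 consecutive months". The control arm receives oral prednisone, "0.4 mg/kg body weight for 2 months and then gradual reduction of 5 mg/day for 4 months", and then RASBs alone to month 36. Section 4.3.1 repeats the prednisone schedule.

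The table captioned "Figure 2B. SPIRIT 2013 STATEMENT OF THE CHRONIGAN STUDY: Time Schedule of the enrolment interventions, assessments and visits of the participants" (Section 4.5) has post-allocation columns t1, t4, t8, t10, t12, t14, t18, t24, t27, t30, t33 and t36. The creatinine, eGFR, proteinuria and adverse-event rows carry a mark in each. The sampling list in Section 9.5 has the same early sequence: "T0,T1,T4,T8,T10,T14,T24,T36 months".

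Section 4.4 gives a different frequency for CHRONiGaN: end points are evaluated three-monthly for the first two years after enrolment and six-monthly after that. These end points include eGFR slope, eGFR decline and the reciprocal-creatinine slope.

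On kidney function, Section 6.1 adds: "Moreover, we will calculate the slope of acute, chronic and total eGFR (51".

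**The concern.** The first months on a new drug are when early changes in renal function and steroid-related events would be looked for. In Figure 2B the only visit before month 4 is t1, which falls in the run-in, when neither study drug is being taken. The next visit after drug start comes four months later.

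Three things are at stake if Figure 2B is followed as printed. No scheduled contact falls in the full-dose prednisone phase after month 4, although sparing patients corticosteroid side effects is a stated reason for the trial (Section 2.1). A creatinine change without symptoms that appears and resolves between months 4 and 8 is not picked up by any scheduled test. And the early on-drug course of eGFR, which an acute slope is meant to describe, has no intermediate value.

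**Working it through.** No power or sample-size formula applies; the check is timeline arithmetic.

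**1. Reproduce the plan's timeline.** From the synopsis and Section 3, the control arm is 4 + 6 + 26 = 36 months and the experimental arm is 4 + 32 = 36 months. Both agree with the t36 end of treatment. Study drug starts at month 4 in both arms. Prednisone is at full dose in months 4 to 6 and is reduced in months 6 to 10.

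**2. Check that the table is intact.** Figure 2B has 12 post-allocation columns, and the creatinine, eGFR, proteinuria and adverse-event rows each have 12 post-allocation marks. Section 9.5 also goes from T4 to T8. The gap is therefore not a column lost in text extraction.

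**3. Compare the two schedules** (month 0 taken as allocation for both):

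| Source | Months | After 4, up to 6 | Strictly between 4 and 8 |
|---|---|---|---|
| Figure 2B | 1, 4, 8, 10, 12, 14, 18, 24, 27, 30, 33, 36 | none | none |
| Section 4.4 | 3, 6, 9, 12, 15, 18, 21, 24, 30, 36 | 6 | 6 |

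The Figure 2B gap is 8 − 4 = 4 months. The first visit on prednisone comes after 4 of its 6 months (67%), that is, 8 − 6 = 2 months into the reduction.

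**4. Neither schedule can simply replace the other.** They share only months 12, 18, 24, 30 and 36. Section 4.4 lacks month 4 (drug start) and month 10 (primary end point); Figure 2B lacks months 3, 6, 9, 15 and 21. Adopting Figure 2B unchanged would leave the month 4 to 8 gap in place.

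**5. Acute slope.** With eGFR at t4 and t8 only, the early on-drug slope is (eGFR at t8 − eGFR at t4) / 4 per month. Suppose an early step of size a is followed by a steady slope b. Then the difference is about a + 4b: one equation with two unknowns. Later visits could supply b, but carrying it back to month 4 is an assumption that no value inside the interval can check.

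**6. Sensitivity to the start date.** If the treatment bar is read as starting at t1, study drug begins at month 5 and the full-dose phase is months 5 to 7. Figure 2B still has no visit in it.

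**7. Sister trial.** Figure 2A (ACiGaN) has visits at t1, t2, t4, t6 and t8. That gives assessments 1, 2 and 4 months after the early steroid start, and 2 and 4 months after the control-arm start.

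**The case against.** The best defence is that Section 4.4 already calls for a month-6 evaluation, and nothing in the protocol ranks Figure 2B above it. That stands, and it is why the finding is a contradiction between two sections rather than a plain omission. It does not remove the problem. Section 4.5 presents Figure 2B as the schedule of assessments and visits, and Section 4.4 speaks of end points, not adverse events.

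A reader might go further in several ways that the document does not support:

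- *That this period goes unobserved, or that events reach the record only through recall at month 8.* Sections 5.3 and 5.3.1 collect adverse events continuously from consent. Section 5.3.4 takes spontaneous reports and observations as well as answers to the open question. Section 5.3.8 requires serious events to be reported within 24 hours. What is missing is a scheduled contact and scheduled tests.
- *That Figure 2B contradicts Section 1.5.* The dapagliflozin entry there ("hypoglycemia (drug suspension), impairment of the renal function (dose reduction or temporary suspension), acute renal failure (drug suspension") lists responses to risks and promises no test frequency. Local monitoring between visits is neither described nor excluded.
- *That the acute slope cannot be estimated.* Section 6.1 defines no acute window, the acute slope is not listed as an end point in Section 4.4, and t4 and t8 do give a two-point change.
- *That the safety comparison is biased in a known direction.* Both arms have the same gap, and no direction or size follows from the document.
- *That the gap can be stated as a share of cumulative prednisone dose.* The interval between the 5 mg reductions is not given, so any share depends on an assumed taper and, with fixed steps, on body weight.

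**Conclusion.** The point holds in this limited form. Figure 2B leaves four months without a scheduled laboratory or adverse-event visit immediately after study-drug start. Section 4.4 implies an evaluation at month 6, so the two must be reconciled. Under Figure 2B as printed, no scheduled visit falls in the full-dose prednisone phase after month 4, no eGFR value lies strictly between months 4 and 8 in up to 150 patients per arm, and the acute slope reduces to a change between two points.

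This rests on drug start at month 4 (the gap also survives a month-5 reading) and on both schedules counting from about the same date. An eGFR effect still present at month 8 would be seen; what is lost is its course before then and any silent change that has resolved. The point does not touch the month-10 proteinuria comparison, for which Figure 2B has a visit. It should be corrected, but it does not threaten the main result.

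**What to change.** Reconcile Figure 2B with Sections 4.4 and 6.1. Show in Figure 2B the evaluation between months 4 and 8 that Section 4.4 already implies (month 6), with creatinine/eGFR and adverse-event assessment marked, at the same time in both arms. Keep t4 and t10, and amend the Section 4.4 frequency so that both places give one list of months.

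The number of visits need not rise. Section 4.4 asks only for six-monthly evaluation after year two, so t27 or t33 could be dropped. The cost is a schedule edit and, if a visit is dropped, one fewer year-three eGFR value for the three-year slope.

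If no such visit is added, state in Section 6.1 that the CHRONiGaN acute slope is a two-point change from month 4 to month 8, or remove it for that trial. This concerns the timing of measurement only; dosing and what is done clinically with a result remain with the investigators.

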4.6 Collection of biological samples

Blood (8 ml) and morning urine (30 ml) samples will be collected from IgAN patients with acute renal lesions enrolled in the ACiGaN clinical study and from IgAN patients with chronic and moderate renal lesions enrolled in the CHRONiGaN trial. Samples will be collected at the time points reported in the *Figure 2A* and *Figure 2B*. Blood and urine samples will be used for cystatin C measurement. The measurement of this variable will permit to obtain the eGFR creatinine/cystatin C, used to better evaluate the renal damage progression.

All samples will be stored in freezer at -20° or -80°C in the participant renal centers. Every six months, or when possible, the collected biological samples will be shipped to the [name] Foundation for the molecular study. Shipping fees will be supported by the Foundation.

For the collection of biological samples for the ancillary study “Cutting-edge bio-molecular analysis for precision therapy in IgAN (BIO-D), please refer section *No. 9. ANCILLARY PROJECT*.

4.7 End of Study and Patient withdraw

The end of the study is defined as the last visit of the last enrolled subject.

A visit of end of study will be performed 30 days after last treatment to collect data about any adverse events and other administered therapies.

The withdraw of enrolled patients from study treatment and/or from the whole study will be done in the following conditions:

- withdraw of the informed consent
- pregnancy
- superimposed malignant diseases
- kidney failure (end-stage kidney disease)
- dialysis
- renal transplant
- non-compliance with study procedures
- Investigator judgment, for any ethical, medical, or scientific reasons
- Death.

The patient may withdraw from the treatment/trial, at any time, without penalty or loss of benefits to which he/she is otherwise entitled.

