4.4 Outcome measures

The primary endpoint is the 24 h-proteinuria reduction between arms as suggested by Inker LA et al (44). It will be assessed after 4 and 8 months in the ACiGaN study and after 10 months in the CHRONiGaN trial.

The secondary end point is the GFR slope calculated as the mean of individual slope obtained from individual linear regression of eGFR overtime (3 years). Based on the International Consensus definition of clinical trial outcomes for kidney failure (23) we have also considered other secondary end points listed below.

Primary and secondary end points that will be evaluated in the two RCTs are listed below:

Primary endpoint:

- Between-arms difference in proteinuria reduction within 4 and 8 months in ACiGaN and within 10 months in CHRONiGaN study.

Secondary endpoints:

- eGFR slope calculated as mean of individual slope obtained from individual linear regression of eGFR overtime (3 years);
- eGFR decline > 40 % from the baseline value;
- composite end point: GFR decline > 40%, ESKD (defined as long-term GFR \leq 15 ml/min/1.73m² for more than three months or need for maintenance dialysis or kidney transplantation) or death due to kidney disease;
- absolute difference between last GFR value and baseline GFR;
- stable renal function defined as a decline in GFR \leq 5 ml/min/1.73m² at the end of three years follow-up;
- mean annual change in the slope of the reciprocal of serum creatinine concentration;
- time-averaged proteinuria (TA-P) calculated as the weighted mean of all post-randomization measurement, with weights representing the time elapsed since the previous measurement;
- proteinuria slope, calculated as a mean of individual slope, obtained from individual linear regression of daily proteinuria overtime (3 years);
- complete remission of proteinuria defined as achievement of urinary protein level \leq 0.2 g/day or a urinary protein-to-creatinine ratio \leq 0.2 g/g;
- partial remission of proteinuria defined as achievement of a urinary protein reduction \geq 50% or greater compared with baseline value.

The end points will be evaluated monthly in IgAN patients with active renal lesions in the first eight months after kidney biopsy and then every three months. In IgAN patients with chronic or moderate renal lesions the end points will be evaluated every three months in the first two years after the enrollment and then every six months.

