6.4 Statistical Methods

Quantitative variables will be summarized in the presence of normal distribution values as mean \pm SD or median, and interquartile ranges in the presence of non-normally distributed variables. The between-arms comparisons of continuous variables will be performed by independent t-test or Mann-Whitney U test, as appropriate. The between-arms difference of the primary end point (i.e. in the between-arms difference of delta 24h proteinuria from baseline to 6 months in the ACiGAN trial and the between-arms difference of delta 24h proteinuria from baseline to 12 months in the CHRONiGAN trial will be expressed as mean difference and 95% CI. Categorical variables will be presented as absolute and percentage frequency. Proportions will be compared using the Pearson's X^2 test or Fisher's test, as appropriate. The time to event analysis will be performed by the Kaplan-Meier curves by comparing the experimental and control group by the log rank test. Multivariate analysis will be based on Cox's regression proportional hazard method and used to assess the relative risk associated with possible baseline prognostic factors such as sex, age, serum creatinine, eGFR, hypertension, histological lesions and therapy.

The primary analysis will be conducted according to the intention-to-treat approach in all randomized patients, irrespective of adherence to the assigned treatment. A per protocol analysis will be also performed. A secondary analysis by linear mixed models (LMM) or generalized estimating equations (GEE) of repeated measurements of eGFR and proteinuria will be also performed. The choice between the two analyses will closely depend on the distribution type of the outcome variables in our study cohorts.

In these models, data will be expressed as regression coefficients, 95% CIs and P value. All analyses will be performed using SPSS for Windows, 17.0 (SPSS Inc., North Sydney, Australia) and STATA/IC 13.1 for Windows (College Station, Texas, US). A *P* value less than 0.05 will be considered statistically significant.

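### Section 4.7 does not separate stopping study treatment from leaving the study, and nothing requires outcome measurement after early stopping, so the ITT analysis is exposed to possibly informative missing data

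*Protocol*

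**What the plan says.** Section 4.7 states: "The withdraw of enrolled patients from study treatment and/or from the whole study will be done in the following conditions". A single list follows, and no item is assigned to treatment only or to follow-up. Besides withdrawn consent, pregnancy, malignancy and death, it contains "non-compliance with study procedures", "Investigator judgment, for any ethical, medical, or scientific reasons", kidney failure, dialysis (with no qualifier) and renal transplant.

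The only contact that section 4.7 ties to the end of treatment is a visit "30 days after last treatment to collect data about any adverse events and other administered therapies". It names neither creatinine nor proteinuria.

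Section 6.4 states: "The primary analysis will be conducted according to the intention-to-treat approach in all randomized patients, irrespective of adherence to the assigned treatment". Section 6.5 repeats that the primary population is everyone randomized. It adds a secondary population of patients who persisted on the drugs, and classes patients who change treatment early as dropouts without saying whether they are still measured.

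The primary endpoint (section 4.4) is the change in 24-hour proteinuria. Secondary endpoints include eGFR and proteinuria slopes over 3 years and a composite. Within that composite, ESKD means GFR of 15 or below for more than three months, or "need for maintenance dialysis or kidney transplantation".

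**The concern.** An ITT analysis needs two things: the set of all randomized patients, and their outcomes whatever happened to treatment. The protocol secures the first. For the second, section 4.7 lets a site end follow-up altogether for reasons that arise after randomization and that treatment may affect.

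Both trials are open-label. ACIgAN compares immediate intravenous pulses plus prednisone with RASBs first and steroids later. CHRONIgAN compares six months of prednisone with dapagliflozin. Section 1.5 lists different harms for each drug. Investigators know the arm and may remove a patient for any ethical, medical or scientific reason, so removal could differ between arms and be related to response. The between-arm proteinuria difference would then partly reflect who stayed, and the 3-year slopes would be cut short in the same patients.

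This belongs in the protocol. An SAP can specify how missing values are handled, but it cannot recover urine collections and creatinine values that were never taken.

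**Working it through.** **1. Is continued measurement required anywhere?**

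- Section 4.7: one list, treatment and/or whole study; the post-treatment visit covers adverse events and therapies.
- Figures 2A and 2B: creatinine, eGFR and daily proteinuria are scheduled to month 36. They are not made conditional on taking the drug, but nothing says they continue after a section 4.7 withdrawal.
- Section 6.2: regular visits and a final outpatient visit, with no rule for patients off treatment.
- Section 7.1: quarterly webinars are the only retention measure.
- Section 6.5: early treatment changers are dropouts.

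None of these requires outcome collection after early stopping, while section 6.4 promises analysis "in all randomized patients, irrespective of adherence to the assigned treatment".

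**2. The plan's own figure (ACIgAN, section 6).** Inputs: mean changes 1.2 and 0.6 g/24 h, SD 1.0, two-sided alpha 0.05, power 90%, dropout 10%.

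n per arm = 2(1.960 + 1.282)² × 1.0² / 0.6² = 58.4, rounded up to 59. With dropout: 59 / 0.90 = 65.6, rounded up to 66 per arm, 132 in total. This reproduces the protocol. CHRONIgAN's 300 is called opportunistic and has no stated effect, SD or power, so there is nothing to reproduce.

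**3. Effect of missing outcomes on power.** Power = Φ(0.6 / √(2/m) − 1.960), with m patients measured per arm out of 66. The 20% and 30% rates are assumed.

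| Missing | m per arm | Power |
|---|---|---|
| 10% (planned allowance) | 59.4 | 90.5% |
| 20% | 52.8 | 86.9% |
| 30% | 46.2 | 82.2% |

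The dropout allowance protects power. It gives no protection against bias.

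**4. Effect on bias (illustration).** Let a share f of one arm be lost, with a mean proteinuria reduction k g/24 h smaller than that of the patients kept (mean M). The full-arm mean is (1 − f)M + f(M − k) = M − fk. The patients kept show M, so the arm's mean is overstated by fk. Values of f and k are assumed.

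| f | k = 0.5 | k = 1.0 |
|---|---|---|
| 5% | 0.025 | 0.05 |
| 10% | 0.05 | 0.10 |
| 20% | 0.10 | 0.20 |

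Against the planned 0.6 difference, the ends of the range are 0.025 / 0.6 = 4% and 0.20 / 0.6 = 33%. If both arms lose patients, the net bias is the difference between the two products fk. It can go either way and is zero when they are equal.

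**5. Dialysis.** The section 4.7 item is unqualified. The composite in section 4.4 needs maintenance dialysis, or low GFR lasting more than three months. On the literal wording, a patient dialysed temporarily could leave before recovery or ESKD is established.

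**The case against.** The strongest reply is that the text permits whole-study withdrawal without requiring it, and that the rest of the protocol points towards continued follow-up. Several parts of this stand.

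- A reader might infer that section 4.7 removes every listed patient from the study. The and/or wording does not support that: each item may end treatment only.
- A reader might infer that ITT cannot be done. The ITT set can still be formed. Section 6.5 separates persisters from all randomized, so non-persisters are expected in the primary set, and section 6.4 adds mixed models or GEE, which can use partial data. Further missing-data handling may be in an SAP that is not shown.
- A reader might infer that anyone who stops steroids has only the 30-day visit left. RASBs are listed among study treatments (section 4.3.1) and run to month 36, and section 4.3.2 foresees rescue therapy without study exit. This mostly stands, although the synopsis names only corticosteroids and dapagliflozin as study products, so last treatment can be read two ways.
- The list does not name intolerance or adverse events, and non-compliance there concerns study procedures. Such cases could enter through investigator judgment, but the documents do not say that withdrawals are caused by treatment.
- ESKD, maintenance dialysis and transplant are composite events themselves, so a first-event analysis counts them. Section 4.3.2 describes dialysis for lasting low eGFR, and temporary dialysis is hypothetical here. The dialysis point is therefore secondary.
- The bias figures rest on assumed, one-sided loss. At f = 10% and k = 0.5 the shift is 0.05 g/24 h, against a standard error of √(2/59) = 0.18.

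The reply does not supply an instruction that outcome visits continue after early stopping. Leaving the choice to unblinded sites, with no criterion, is the defect.

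**Conclusion.** The point holds as a defect in a stated rule. Section 4.7 merges two kinds of withdrawal, allows study exit for non-compliance with procedures and for investigator judgment, and no section requires outcome data afterwards. The ITT analysis in sections 6.4 and 6.5 and the 3-year eGFR and proteinuria endpoints are therefore exposed to missing data that may be informative.

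The size is unknown from the documents. The range of 0.025-0.20 g/24 h is an illustration for one ACIgAN arm. It assumes 5-20% loss in that arm, lost patients 0.5-1.0 g/24 h worse, an analysis that rests on the patients kept, and no offsetting loss in the other arm. The same wording governs CHRONIgAN, but no planned difference is stated there to scale against.

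The unqualified dialysis item and the composite definition should also be reconciled.

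**What to change.** Split section 4.7 into two lists.

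- **(a) Conditions under which study treatment may stop.** The clinical content is for the sponsor to decide.
- **(b) Conditions that end follow-up.** Limit these to withdrawal of consent to follow-up, death and loss to follow-up.

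State that patients under (a) who are not under (b) keep the Figure 2A or 2B creatinine and 24-hour proteinuria visits to month 36. After dialysis or transplant, record renal replacement status (temporary or maintenance) and vital status. Reconcile the dialysis item with the composite definition in section 4.4. In section 6.5, say that patients classed as dropouts are still measured.

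The cost is amendment wording and some effort to keep contact with patients who are off treatment. The visits are already in the schedule. Values missed before the change cannot be recovered, so an early amendment is preferable.
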